15.4 New York Heart Association Classification of Cardiac Disease

The following table presents the New York Heart Association classification of cardiac diseases.

Class	Functional Capacity	Objective Assessment
I	Patients with cardiac disease but without resulting limitations of physical activity. Ordinary physical activity does not cause undue fatigue, palpitation, dyspnea, or anginal pain.	No objective evidence of cardiovascular disease.
II	Patients with cardiac disease resulting in slight limitation of physical activity. They are comfortable at rest. Ordinary physical activity results in fatigue, palpitation, dyspnea, or anginal pain.	Objective evidence of minimal cardiovascular disease.
III	Patients with cardiac disease resulting in marked limitation of physical activity. They are comfortable at rest. Less than ordinary activity causes fatigue, palpitation, dyspnea, or anginal pain.	Objective evidence of moderately severe cardiovascular disease.
IV	Patients with cardiac disease resulting in inability to carry on any physical activity without discomfort. Symptoms of heart failure or the anginal syndrome may be present even at rest. If any physical activity is undertaken, discomfort is increased.	Objective evidence of severe cardiovascular disease.

15.5 Steroid Equivalent Doses

Approximately equivalent doses:

Steroid	Glucocorticoid Anti-inflammatory (mg)	Mineralicorticoid (mg)	Half-life (hours)
Cortisone	100	100	8–12
Hydrocortisone	80	80	8–12
Prednisone	20	100	12–36
Prednisolone	20	100	12–36
Methylprednisolone	16	no effect	12–36
Dexamethasone	2	no effect	36–72

Source: Knoben JE, Anderson PO. Handbook of Clinical Drug Data, 6th ed. Drug Intelligence Pub, Inc. 1988.⁽⁶⁴⁾

CCI

s of Use

Property of

Property of
Cassling

Use

15.7 Amyloid-Related Organ Involvement

Renal	Albuminuria >0.5 g/day in a 24-hour urine collection
Cardiac	
The presence of a mean left ventricular wall thickness on echocardiogram >12 mm in the absence of a history of hypertension or valvular heart disease, or of unexplained low voltage (<0.5 mV) on the electrocardiogram; or
 
NT-proBNP > 332 ng/L in the absence of renal failure (eGFR <45 mL/min/1.73 m²).
 
Clinical status is based on history, physical examination, and New York Heart Association (NYHA) heart failure class. Patients who are NYHA class 1 with evidence of cardiac amyloid by echocardiogram or electrocardiogram are categorized as having asymptomatic cardiac instability. Patients who are NYHA class 2 or higher with evidence of cardiac instability are categorized as having dominant cardiac instability (amyloid cardiomyopathy).

Hepatic and gastrointestinal	Hepatic involvement is defined as hepatomegaly on physical examination with an alkaline phosphatase value >1.5 × ULN. Gastrointestinal involvement is defined as direct biopsy verification of amyloid with symptoms such as gastrointestinal bleeding confirmed by tissue biopsy and diarrhea > 4 stools/ day over patient's baseline.
Autonomic and/or peripheral neuropathy	Neuropathic involvement is defined based on clinical history, autonomic dysfunction with orthostasis, symptoms of nausea or dysgeusia, gastric atony by gastric emptying scan, diarrhea or constipation, or abnormal sensory or motor findings, or both, on neurological examination.
Soft tissue and lymphatic	Involvement may be ascertained based on classic physical examination findings (macroglossia, shoulder pad sign, raccoon eyes, carpal tunnel syndrome, synovial enlargement, firm enlarged lymph nodes) or biopsy.

15.8 Assessment of Hematologic Disease Response

The definition of hematologic response to treatment is based on the difference between the concentration of amyloid forming (involved) and uninvolved free light chain (dFLC).

To be measurable dFLC must be at least 50 mg/L. Patients with dFLC < 50 mg/L are eligible for clinical studies but are evaluable only for complete remission.

Complete Response (CR)	Serum and urine negative for monoclonal protein by immunofixation; or free light chain ratio normal. $<5\%$ plasma cells in bone marrow without clonal dominance
Very Good Partial Response (VGPR)	dFLC < 40 mg/L
Partial Response (PR)	Reduction in dFLC $> 50\%$
Progressive Disease (PD)	Is a 50% increase in serum M-protein to >0.5 g/dL from nadir/baseline, or 50% increase in urine M-protein to >200 mg/24 hours with a visible peak present; free light chain increase of 50% from nadir or baseline to >10 mg/dL (100 mg/L) Following a response of CR, the appearance of any detectable monoclonal protein by immunofixation, or abnormal free light chain ratio (light chain must double)

Source: Gertz et al. Definition of organ involvement and treatment response in immunoglobulin light chain amyloidosis (AL): A consensus opinion from the 10th International Symposium on amyloid and amyloidosis ⁽⁵⁴⁾

Modified criteria proposed by the 2010 International Society of Amyloidosis Consensus ^(55, 56)

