The estimated safe starting dose of MLN9708 will be selected from the dose-escalation portion of

the C16004 study, a phase 1 study of weekly dosing in patients with relapsed and refractory multiple myeloma. The starting dose will be at least 1 dose level below the C16004 MTD (if it has been reached by the time this study starts) and, if not, then a dose level completed without documented dose-limiting toxicity (DLT).

DLTs will be assessed in Cycle 1 only. In the context of emerging clinical data of single-agent MLN9708, dose-escalation of MLN9708 will continue until the MTD has been identified or a maximum planned dose (MPD) is determined to be safe.

Once the MTD/RP2D has been established, 2 expansion cohorts of patients with relapsed or refractory amyloidosis, including approximately 10 proteasome inhibitor-naïve patients and approximately 16 proteasome inhibitor-exposed patients, will be treated at the MTD/RP2D to more fully characterize the safety, tolerability, and efficacy of MLN9708, and the PK and pharmacodynamics of MLN9708 in this patient population. As many as 30 patients will be enrolled in the dose-escalation portion of the study, and as many as 20 additional patients (26 in total, including 6 patients from the dose-escalation portion) will be enrolled in the expansion cohorts.

Toxicity will be evaluated according to the investigators' documentation of adverse events (AEs) using the National Cancer Institute Common Terminology Criteria for Adverse Events, version 4.03. AEs will be assessed, and laboratory values, vital signs, and ECGs will be obtained to evaluate the safety and tolerability of MLN9708.

Patients will be evaluated at scheduled visits over 4 study periods: Screening, Treatment, End of Treatment (EOT), and Follow-up (progression-free and overall survival). Patients will discontinue treatment if they experience PD or unacceptable toxicity. The maximum duration of treatment with either single-agent MLN9708 or MLN9708 plus dexamethasone, however, will be 12 cycles unless after discussion between the investigator and the sponsor, it is determined that a patient would derive benefit from continued therapy beyond 12 cycles.

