5.8 Efficacy Endpoints and Analyses

Standard response criteria will be used in this study. The efficacy parameters include hematologic response rate, organ response rate, time to hematologic response, time to organ response, duration of hematologic response, duration of organ response, time to hematologic

disease progression, time to organ disease progression, hematologic disease PFS, organ disease PFS, and 1-year overall survival (OS) rate. The response assessment criteria are defined in the study protocol appendices.

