the date of first documentation of an organ response of either heart or kidney. In addition, time to best hematologic response is defined as the time from the date of the first dose of MLN9708 to the date of first documentation of the best hematologic response for each patient. The time-to-response endpoints apply only to the responders; therefore, there is no censoring. Hematologic responder is defined as a patient whose best hematologic response is PR or better. Vital organ responder is defined as a patient who demonstrates vital organ response. In addition, the responders will be determined in 2 time frames: (1) Up to the EOT visit; and (2) Up to the initiation of alternative antineoplastic therapy or EOS.

Duration of hematologic response is defined as the time from the date of first documentation of a hematologic response (PR or better) to the date of hematologic PD. Duration of vital organ response is defined as the time from the date of first documentation of an organ response of either heart or kidney to the date of organ PD. The duration-of-response endpoints apply only to the responders. However, the responders will be determined in two time frames: (1) Up to the EOT visit; and (2) Up to the initiation of alternative antineoplastic therapy or EOS. Patients will be censored in any of the following scenarios:

- If the patient starts an alternative antineoplastic therapy before the documentation of PD, then he or she will be censored at the date of the last available response assessment before the alternative antineoplastic therapy.
- If the patient has no documented PD and has not started alternative antineoplastic therapy and is still alive at the time of analysis, he or she will be censored at the date of the last available response assessment.
- If the patient died before the documentation of PD and had not started any alternative antineoplastic therapy, he or she will be censored at the date of the last available response assessment.

Time to hematologic disease progression is defined as the time from the date of the first dose of MLN9708 to the date of first documented hematologic PD. Time to organ disease progression is defined as the time from the date of the first dose of MLN9708 to the date of first documented organ PD. Patients will be censored in any of the following scenarios:

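### Protocol 15.8 lets one assessment after a complete response count as both complete response and progression, and neither document says which prevails

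*Protocol*

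**What the plan says.** Protocol 15.8 defines hematologic response in one table.

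- **CR row:** "Serum and urine negative for monoclonal protein by immunofixation; or free light chain ratio normal". The same cell adds fewer than 5% "plasma cells in bone marrow without clonal dominance", with no connecting word between the two parts.
- **PD row, last clause:** this applies only after a CR. It counts "the appearance of any detectable monoclonal protein by immunofixation, or abnormal free light chain ratio" as progression. A parenthesis on the ratio limb adds that the light chain must double.

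The SAP sets no criteria of its own. Section 5.8 states: "The response assessment criteria are defined in the study protocol appendices". SAP 5.8.1 then builds the CR rate, the VGPR-or-better rate, the overall response rate, duration of hematologic response, time to hematologic PD and hematologic PFS on those categories. Neither SAP 5.8.1 nor Protocol 8.1.6 has a rule for an assessment that meets two categories.

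The categories also steer treatment. The Protocol Summary states: "Patients will discontinue treatment if they experience PD or unacceptable toxicity". Protocol 4.1 uses the presence or absence of hematologic response to decide whether dexamethasone is added from Cycle 4, and whether a patient leaves treatment after three further cycles.

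**The concern.** A response category and the rule for losing it should not overlap. Here a patient enters CR by holding either marker but progresses by losing either one. A patient who holds one marker and loses the other falls under both rows.

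Three things are at stake.

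- **Event dates.** If PD prevails, duration of response ends at that visit, and time to hematologic PD and hematologic PFS each gain an event. If CR prevails, all three continue. Two programmers could follow the same text and produce different curves.
- **Response rates.** The overlap arises only after a CR, so best response is already CR and the later label does not change it. The repair can change it, because a stricter CR row reclassifies patients who met only one marker.
- **Data that cannot be recovered.** A PD call ends treatment. Under Protocol 7.5.17 it also ends organ follow-up, since progression there includes hematologic progression. It counts toward the trigger for the study report too (75% of patients with PD, or 12 months after the last enrollment, whichever is first; Protocol 4.3, SAP 5). Reanalysis cannot restore assessments that were never made.

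**Working it through.** The plan gives no figure on this point, so the check is one of logic.

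**Inputs (Protocol 15.8).** Immunofixation is negative or positive. The free light chain ratio is normal or abnormal. The light chain has doubled or has not. Marrow plasma cells are held below 5% at both visits, so that condition is always met.

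**Rules.**
- CR as written: immunofixation negative *or* ratio normal.
- PD after CR as written: monoclonal protein appears by immunofixation, *or* the ratio is abnormal and the light chain has doubled.
- Appearance is read two ways: newly positive since the previous visit, or any detectable protein.

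**Count.** Three of the four marker states at visit 1 are CR. With four states at visit 2 and two doubling states, 3 × 4 × 2 = 24 sequences start in CR. With appearance read as newly positive, these meet both rows at visit 2:

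| Visit 1 | Visit 2 | Light chain doubled | CR through | PD through | Sequences |
|---|---|---|---|---|---|
| negative, normal | positive, normal | yes or no | ratio | immunofixation | 2 |
| negative, normal | negative, abnormal | yes | immunofixation | ratio | 1 |
| negative, abnormal | positive, normal | yes or no | ratio | immunofixation | 2 |
| negative, abnormal | negative, abnormal | yes | immunofixation | ratio | 1 |
| positive, normal | negative, abnormal | yes | immunofixation | ratio | 1 |

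Total: 2 + 1 + 2 + 1 + 1 = 7. If any detectable protein counts, positive/normal followed by an unchanged positive/normal adds 2, giving 9. These are counts of logical possibilities, not probabilities.

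**With *and* in the CR row.** Visit 2 is CR only if immunofixation is negative and the ratio normal, so neither limb of the post-CR clause can be met. The count is 0 on either reading of appearance.

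**Can overall response change?** Take an illustrative patient with baseline dFLC 60 mg/L, now 45 mg/L, immunofixation negative, ratio abnormal and marrow below 5%. As written this is CR. If both markers were required it would not be CR. It would not be VGPR, because 45 is not below 40. It would not be PR, because the reduction is (60 − 45)/60 = 25%, not more than 50%. The patient becomes a non-responder. Separately, inclusion criterion 3 admits patients with dFLC of at least 40 mg/L, while Protocol 7.5.12.1 and 15.8 make those below 50 mg/L evaluable only for CR. For patients from 40 to below 50 mg/L, the CR row is the whole response definition.

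The check covers the post-CR clause only, not the M-protein and light chain increase limbs of the PD row.

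**The case against.** The best defense is that CR followed by PD is an ordinary course. SAP 5.8.1 takes best response over time and ends duration at hematologic PD, so an analyst could apply both without trouble. That is a sensible convention, but it amounts to letting PD prevail, and neither document says so. The protocol's use of confirmed response and confirmed progression (3.2, 8.1.6) does not settle it, because a stable discordant result would confirm both categories.

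A second defense is the marrow condition. Marrow is not scheduled every cycle, so a later visit may lack the evidence to meet the CR row again. This may make the overlap rarer. It does not remove it, since a patient with marrow below 5% still meets both rows.

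Some stronger readings are tempting, and the objections to them stand.

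- A reader might infer that the result establishing CR is itself PD, or that a patient with a normal ratio and persistently positive immunofixation has a response of zero duration. The post-CR clause needs a CR beforehand and the appearance of protein. Protein present throughout has not appeared in the ordinary sense. Even on the loose reading, PD needs a later assessment.
- A reader might infer that the table's own logic requires both markers for CR. It does not. A sponsor may choose an easy entry rule with a strict relapse rule, provided it says which prevails.
- A reader might infer that only the CR rate moves and overall response is safe. The dFLC example shows otherwise.

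**Conclusion.** The two rows are inconsistent as written. After a CR, a single later assessment can satisfy CR through the retained marker and PD through the lost one, on the strictest reading of appearance and with the marrow condition met. The SAP inherits the conflict and does not resolve it.

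Duration of hematologic response, time to hematologic PD and hematologic PFS are directly affected. The CR, VGPR-or-better and overall response rates depend on how the rows are reconciled. All are secondary endpoints. The dose-limiting toxicity count that sets the MTD does not use these rows.

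The size cannot be estimated. The documents give no rate of discordant immunofixation and ratio results and no expected number of CRs, so they do not support a claim that the CR rate is inflated by a given amount. For scale only, and assuming every enrolled patient is evaluable, each reclassified patient moves a response rate by 1/50 = 2 percentage points at maximum enrollment, 1/16 = 6.25 points in the proteasome inhibitor-exposed cohort and 1/10 = 10 points in the naïve cohort.

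**What to change.** Reconcile the CR row and the post-CR PD clause in Protocol 15.8 so that no assessment can satisfy both. There is more than one coherent way:

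- Require both markers for CR, which removes every overlap found above.
- If *or* is intended, rewrite the post-CR PD clause to match, and test the new wording against the sequences in the table.
- Keep both rows and state which category takes precedence.

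State also whether appearance means newly positive since the CR, and carry the same rule into SAP 5.8.1. Because these categories decide continuation of treatment and the addition of dexamethasone, the choice of criterion belongs to the sponsor and its clinical advisers. The statistical requirement is only that the rows be mutually exclusive or ordered.

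The cost is a short amendment to the appendix and matching SAP text. Immunofixation and the free light chain ratio are already measured on Days 22 to 28 of every cycle (Protocol 7.5.12.1), so no test is added. If both markers are required, the CR rate and possibly the overall response rate may be slightly lower, and some patients could be classified differently at the Protocol 4.1 decision points.

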15.9 Criteria for Treatment Response of Amyloid-Related Organs

Response

Heart

NT-proBNP reduction $\geq 30\%$ and ≥ 300 ng/L in patients with eGFR ≥ 45 mL/min/1.73 m²; baseline NT-proBNP must be at least 650 ng/L to be measurable, or

A decrease in mean interventricular septal thickness by 2 mm, or 20% improvement in ejection fraction, or

Improvement in NYHA classification by 2 classes without an increase in diuretic use, and no increase in wall thickness

Kidney

At least a 50% decrease in 24-hour urine total protein (urine protein must be > 0.5 g/24 hours before treatment) in the absence of a reduction $\geq 25\%$ in eGFR and a 0.5 mg/dL increase in serum creatinine

Liver

At least a 50% decrease in abnormal alkaline phosphatase value

Decrease in liver size of at least 2 cm assessed in individual patients either by physical exam or radiographically. (Note: The same evaluation [physical examination or radiography] must be used consistently in individual patients throughout the study)

Nerve

No reliable method for defining peripheral and autonomic nervous system response.

Improvement in clinical examination findings

Decrease in the reported Neurotoxicity score^a

Improvement in orthostatic blood pressure

Improvement in any symptoms and/or signs related to peripheral

Disease Progression^a

NT-prBNP increase $\geq 30\%$ and ≥ 300 ng/L in patients with eGFR ≥ 45 mL/min/1.73 m², or

An increase in interventricular septal thickness by 2 mm compared with baseline, or

An increase in NYHA classification by 1 class with a decrease in ejection fraction of at least 10%

50% increase (at least 1 g/day) in 24-hour urine total protein to > 1.0 g/24 hours or

25% worsening of serum creatinine or creatinine clearance (or eGFR).

50% increase in alkaline phosphatase value as compared with the lowest value, or

An increase in liver size by at least 2cm (radiographic determination)

Progressive neuropathy (peripheral, cranial or autonomic) not attributable to MLN9708 in the opinion of the investigator

neuropathy, cranial neuropathy, or other autonomic dysfunction

Decrease in neuropathic pain

GI

Reduction of diarrhea to less than 50% of previous movements/day or decrease in fecal fat excretion by 50%

Worsening of diarrhea with increase $>$ than 50% of previous movements/ day not attributable to MLN9708 in the opinion of the investigator or fecal fat by 50%

Source: Gertz et al. Definition of organ involvement and treatment response in immunoglobulin light chain amyloidosis (AL): A consensus opinion from the 10th International Symposium on amyloid and amyloidosis. Am J Hematol 2005; 79: 319-328⁽⁵⁴⁾
Modified criteria proposed by the 2010 International Society of Amyloidosis Consensus. ⁽⁵⁵⁾

- a Organ progression can occur in an organ that has not been involved at baseline.
- b Based on NCI CTC Version 4.02 criteria. ⁽⁶⁵⁾

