
Note: The average of the estimates of the interventricular septal and posterior wall thickness yields the mean ventricular wall thickness.

Note: If CT or MRI cardiac assessments are clinically indicated, then a record of the findings will be made.

Renal Assessment:

- 24-hour urine collection (total protein, M-protein quantification, and immunofixation)
- eGFR assessment

- Serum creatinine
- Serum albumin

Renal assessments are to be performed in all patients as outlined in the [Schedule of Events](#).

Hepatic Assessment

- Alkaline phosphatase
- Clinical examination, or
- Abdominal ultrasound, or
- CT or MRI scans at the discretion of the investigator as clinically indicated.

Hepatic assessments are to be performed in all patients as outlined in the [Schedule of Events](#). The same evaluation (physical examination or radiography [and the same imaging modality]) must be used consistently in individual patients throughout the study for all follow-up assessments.

Neurologic Assessments

Assessments are to be performed in all patients as outlined in the Schedule of Events.

- Patient-reported gastrointestinal and neurologic symptoms
- Clinical examination
- Neurologic examination, including sensory and/or motor findings
- Nerve conduction studies, if indicated (including electromyography, if necessary)
- Detection and measures of postural hypotension

Soft Tissue or Lymph Node

Assessments are to be performed in all patients as outlined in the [Schedule of Events](#).

- CT or MRI scans at the discretion of the investigator as clinically indicated. The same imaging modality used at screening (CT/MRI) should be used for all follow-up assessments
- Recording of any abnormalities on physical examination

- Patient reported symptoms

The investigator will evaluate each patient for response to therapy according to the response criteria presented in Sections 15.8 and 15.9. At each staging evaluation, the organ response will be assessed relative to baseline.

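### Protocol 15.9 lets a liver-size decrease be scored by physical exam or radiography but an increase only by radiography, while each patient is bound to one method, so exam-followed patients cannot meet size-based progression

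*Protocol*

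**What the plan says.** Protocol 15.9 sets out liver response and liver progression in adjacent columns. The size item for response reads "Decrease in liver size of at least 2 cm assessed in individual patients either by physical exam or radiographically". The size item for progression reads "An increase in liver size by at least 2cm (radiographic determination"). The note attached to the response item adds: "The same evaluation [physical examination or radiography] must be used consistently in individual patients throughout the study".

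The Hepatic Assessment part of Protocol 7.5.12.2 repeats the one-method rule and extends it to all follow-up: "The same evaluation (physical examination or radiography [and the same imaging modality]) must be used consistently in individual patients throughout the study". The same list offers clinical examination, abdominal ultrasound or cross-sectional imaging as alternatives, the last being "CT or MRI scans at the discretion of the investigator as clinically indicated".

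Baseline liver involvement does not need an image. Under Protocol 15.7, "Hepatic involvement is defined as hepatomegaly on physical examination" together with a raised alkaline phosphatase.

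The progression column has a second route, a 50% rise in alkaline phosphatase over its lowest value, joined to the size item by an explicit or. SAP 5.8 refers to the protocol appendices for response criteria and adds no liver rule of its own.

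**The concern.** A rule for measuring change should treat both directions alike within a patient. Here the permitted method depends on the direction of change, and a separate rule stops the patient from moving to the other method. Two patients whose livers enlarge by the same amount can be classified differently only because one was imaged at baseline and the other examined.

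The error runs one way: a size-based progression can be missed, or dated later when another criterion is met. Liver PD is a planned output, because SAP 5.8.1 calculates organ-specific rates, with PD as a category, in patients with that organ involved. Organ PD also supplies the event date for several secondary endpoints, and the SAP text does not restrict organ PD to heart or kidney.

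**Working it through.** No figure in the plan needs reproducing, and no sample size, power or event count enters. The check sets the passages side by side.

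1. Size response (15.9): exam or radiography.
2. Size progression (15.9): radiography only.
3. Method per patient (15.9 note; 7.5.12.2 Hepatic Assessment): one, kept throughout.
4. Exam as the only method (7.5.12.2): permitted. Baseline involvement (15.7) rests on exam plus alkaline phosphatase, so a baseline image need not exist.
5. Other route to liver progression (15.9): alkaline phosphatase, open whatever the imaging.

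Combining items 1 to 5:

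| Method fixed for the patient | Size component of response | Size-based progression | Progression by alkaline phosphatase |
|---|---|---|---|
| Radiography | can be met | can be met | can be met |
| Physical exam | can be met | cannot be met | can be met |

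The one empty cell is the defect. It could be filled only by reading the radiographic qualifier as overriding the one-method rule. Neither section says that, and an exam-followed patient may have no baseline image from which to measure 2 cm. A footnote to 15.9 also allows progression in an organ not involved at baseline, where a baseline liver image is less assured still.

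Next, where the empty cell reaches the analysis:

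- Liver-specific PD category (SAP 5.8.1): affected. The rate uses best response over time, so a patient who first responds and then enlarges is not counted as PD under either rule.
- Time to organ PD and organ PFS (SAP 5.8.1): the event date can be missed or late. SAP 5.8.2 names these endpoints for by-patient listings. Its Kaplan-Meier list contains only hematologic endpoints and OS. Protocol 8.1.6 says such analyses may be done.
- Duration of vital organ response (SAP 5.8.1): starts only from a heart or kidney response and ends at organ PD. It is touched only if a heart or kidney responder has a liver PD that goes unscored.
- Vital organ response rate: heart or kidney only, so unaffected.

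**The case against.** The best defence is that imaging for progression is deliberate. Exam is imprecise, PD is a listed reason to stop treatment, and 15.9 attributes its criteria to published consensus sources that cannot be seen here. That would be a defensible choice, but the plan would then need a baseline liver image in the relevant patients and an exception to the one-method rule. It has neither.

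A second defence is that the exam-only group may be small or empty. The Schedule of Events has a CT/MRI row that names the liver. Its footnotes tie it to the organ-assessment visits and exempt liver monitoring from the rule that repeat scans are discretionary. The plan therefore anticipates serial liver imaging in some patients. This limits the reach of the point, but 7.5.12.2 still permits exam alone.

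A third is that other routes would usually capture the event. Every patient must have heart or kidney involvement, and organ PD can come through those organs or through alkaline phosphatase. A missed event needs at least 2 cm of enlargement with none of these at or before it. This stands, and it dilutes the effect on pooled organ endpoints.

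A reader might infer more than the text supports:

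- That exam-followed patients cannot have liver progression at all. The alkaline phosphatase route refutes this.
- That losing a liver-size response lengthens duration of organ response. It does not, because that endpoint never starts from a liver response.
- That one missed event moves the liver PD rate by a large, quotable percentage. Any such figure rests on invented denominators.
- That the whole liver rule favours response over progression. No connector is visible between the two liver response items. If both are required, an exam-measured decrease alone is not a response. The mismatch in method for the size item remains on either reading.

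**Conclusion.** The point holds for the liver-size item and no further. As written, an exam-followed patient can satisfy the size component of liver response and cannot satisfy size-based progression, and neither the SAP nor the Schedule footnotes resolve this. The direction is missed or later liver progression.

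The size cannot be computed: the documents give no number of patients with liver involvement and no number followed by exam. Protocol 1.1.1 describes liver involvement as uncommon, so the practical effect is probably small. The conclusion assumes that the one-method rule means what it says and that at least some patients are followed by exam alone. The primary endpoints on safety and MTD/RP2D do not turn on it directly, and the vital organ response rate is unaffected. It is a cheap correction worth making to a secondary endpoint definition.

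**What to change.** Reconcile the liver progression line in Protocol 15.9 with the response line beside it and with the one-method rule in 15.9 and 7.5.12.2, so that liver-size change in both directions is judged by the same method used for that patient at baseline. Because PD also bears on stopping treatment, which method to accept is for the sponsor to settle. The statistical requirement is only that the three passages agree. SAP 5.8 needs no change, since it takes its criteria from the appendices.

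The cost is one line of text. If exam is accepted for both directions, no new tests are needed and exam-based progression is less precise, a loss the response column already accepts. If imaging is kept for progression, the text must secure a comparable baseline image and the one-method rule must say how it applies.

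Do not add an or between the two liver response items as part of this change. If both are currently required, that would loosen the response definition and could raise the liver response rate, which is a separate question.
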